3.1 Study Design

QHD04 will be a Phase II, randomized, staged, modified double-blind, active-controlled, multi-center study to be conducted in 700 children 6 months to 17 years of age to evaluate the safety and immunogenicity of 3 dosages of QIV-HD administered by intramuscular (IM) route versus QIV-SD or adjuvanted TIV.

The study will be divided into 13 groups and will enroll in 4 stages. The study will use a stepwise age de-escalation and dose ascension design for children 6 months to < 5 years of age.

Children 5 to 8 years of age will also undergo a dose ascension design and begin enrollment in Stage 1. Children 9 to 17 years of age will be enrolled in Stage 1 and randomized to receive all 3 dose formulations (ie, 30 µg, 45 µg, and 60 µg HA/strain/dose). An early safety data review (ESDR) will be conducted after Visit (V) 02 (at Day [D] 8 post-vaccination) of Stages 1, 2, and 3 for children 6 months to < 5 years of age and Stages 1 and 2 for children 5 to 8 years of age. The ESDR for children 6 months to < 5 years of age will be independent of the ESDR for children 5 to 8 years of age. Enrollment of subjects in the next stage will be initiated if the safety review results are satisfactory.

The 13 study groups are divided according to:

- Age (9 to 17 years^a, 5 to 8 years^b, 36 months to < 5 years, 6 to < 36 months, or 6 to < 24 months)
- Influenza vaccination history (previously influenza vaccinated, previously influenza unvaccinated, or both)
- Administered vaccines (QIV-HD dosages [30 µg, 45 µg, or 60 µg HA/strain/dose], unadjuvanted QIV-SD, and adjuvanted TIV).

The study design and the safety reviews are described in Table 5.1 and Section 5.1.6 of the protocol, respectively. The study flow chart is outlined in [Figure 3.1](#), [Figure 3.2](#), and [Figure 3.3](#). The details of the study design are described below.

Stage 1 will include 3 age groups (36 months to < 5 years, 5 to 8 years, and 9 to 17 years) and will be conducted in the US:

- Previously influenza vaccinated and unvaccinated subjects 36 months to < 5 years of age (Group 1) will be randomized to receive either QIV-HD at 30 µg HA/strain/dose or the unadjuvanted QIV-SD. Based on the early safety data review, the study will either stop (Group 1 does not pass safety review) or continue into Stage 2 .
- Previously influenza vaccinated and unvaccinated subjects 5 to 8 years of age (Group 9), will be randomized to receive either QIV-HD at 30 µg HA/strain/dose or the unadjuvanted QIV-SD. Based on the early safety data review, the enrollment of this age group will either stop (Group 9 does not pass safety review) or continue into Stage 2.
- Previously influenza vaccinated and unvaccinated subjects 9 to 17 years of age (*hereafter referred to as subjects 9 to 17 years of age*) will be divided into 2 groups (Group 12 and Group 13). Group 12 will be enrolled first and will be randomized to receive either QIV-HD at 30 µg, or 45 µg HA/strain/dose or the unadjuvanted QIV-SD. Once the enrollment of Group 12 is complete, subjects in Group 13 will be randomized to receive either QIV-HD at 60 µg or the unadjuvanted QIV-SD. Subjects 9 to 17 years of age will not undergo an ESDR.

Stage 2 will include 3 age groups (6 to < 36 months, 36 months to < 5 years, and 5 to 8 years) and will be conducted in the US:

- Previously influenza vaccinated and unvaccinated subjects 36 months to < 5 years of age (Group 2) will receive either QIV-HD at 45 µg HA/strain/dose or the unadjuvanted QIV-SD and previously influenza vaccinated and unvaccinated subjects 6 to < 36 months of age (Group 3) will receive either QIV-HD at 30 µg HA/strain/dose or the unadjuvanted QIV-SD. Based on the early safety data review, the study will either stop (Group 3 does not pass safety review), continue and skip to Stage 4 (Group 2 does not pass safety review), or continue to Stage 3 (Group 2 and Group 3 both pass the safety review).

^a “9 to 17 years” means from the 9th birthday to the day before the 18th birthday.

^b “5 to 8 years” means from the 5th birthday to the day before the 9th birthday.

- Previously influenza vaccinated and unvaccinated subjects 5 to 8 years of age (Group 10), will be randomized to receive either QIV-HD at 45 µg HA/strain/dose or the unadjuvanted QIV-SD. Based on the early safety data review, the enrollment of this age group will either stop (Group 10 does not pass safety review) or continue into Stage 3.

Stage 3 will include 3 age groups (6 to < 36 months, 36 months to < 5 years, and 5 to 8 years) and will be conducted in the US:

- Previously influenza vaccinated and unvaccinated subjects 36 months to < 5 years of age (Group 4) will receive either QIV-HD at 60 µg HA/strain/dose or the unadjuvanted QIV-SD; and previously influenza vaccinated and unvaccinated subjects 6 to < 36 months of age (Group 5) will receive either QIV-HD at 45 µg HA/strain/dose or the unadjuvanted QIV-SD. Based on the early safety data review, the highest dosage with an acceptable safety review will be determined and used in Stage 4.
- Previously influenza vaccinated and unvaccinated subjects 5 to 8 years of age (Group 11) will be randomized to receive either QIV-HD at 60 µg HA/strain/dose or the unadjuvanted QIV-SD.

Stage 4 will include 2 age groups (6 to < 36 months and 6 to < 24 months) and will be conducted in the US (subjects 6 to < 36 months) and Canada (subjects 6 to < 24 months):

- Previously influenza unvaccinated subjects 6 to < 36 months of age (Group 6) and previously influenza vaccinated subjects 6 to < 36 months of age (Group 7) will be randomized to receive either the highest dosage of QIV-HD with an acceptable safety review or the unadjuvanted QIV-SD.
- Previously influenza unvaccinated subjects 6 to < 24 months of age (Group 8) will receive either the highest dosage of QIV-HD with an acceptable safety review or the adjuvanted TIV.

Table 3.1: Description of study design

Stage (Country)	Age Group (Vaccination Status*)	Study Grou p	N	Vaccine	Vaccine Dosage (μ g HA/strain/dose) †
1 (US)	9 to 17 years (previously vaccinated and unvaccinated)	12	30	QIV-HD	30
			30	QIV-HD	45
			10	unadjuvante d QIV-SD	15
	9 to 17 years (previously vaccinated and unvaccinated)	13	30	QIV-HD	60
			30	unadjuvante d QIV-SD	15
	5 to 8 years (previously vaccinated and unvaccinated)	9	30	QIV-HD	30
			10	unadjuvante d QIV-SD	15
	36 months to < 5 years (previously vaccinated and unvaccinated)	1	30	QIV-HD	30
			10	unadjuvante d QIV-SD	15
2 (US)	5 to 8 years (previously vaccinated and unvaccinated)	10	30	QIV-HD	45
			10	unadjuvante d QIV-SD	15
	36 months to < 5 years (previously vaccinated and unvaccinated)	2	30	QIV-HD	45
			10	unadjuvante d QIV-SD	15
	6 to < 36 months (previously vaccinated and unvaccinated)	3	30	QIV-HD	30
			10	unadjuvante d QIV-SD	15
3 (US)	5 to 8 years (previously vaccinated and unvaccinated)	11	30	QIV-HD	60
			30	unadjuvante d QIV-SD	15
	36 months to < 5 years (previously vaccinated and unvaccinated)	4	45	QIV-HD	60
			45	unadjuvante d QIV-SD	15

Stage (Country)	Age Group (Vaccination Status*)	Study Grou p	N	Vaccine	Vaccine Dosage (μ g HA/strain/dose) †
	6 to < 36 months (previously vaccinated and unvaccinated)	5	30	QIV-HD	45
			10	unadjuvante d QIV-SD	15
4 (US)	6 to < 36 months (previously unvaccinated)	6	30	QIV-HD	30, 45, or 60†
			30	unadjuvante d QIV-SD	15
	6 to < 36 months (previously vaccinated)	7	30	QIV-HD	30, 45, or 60†
4 (Canada)	6 to < 24 months (previously unvaccinated)	8	30	adjuvanted TIV	7.5

Abbreviations: HA, hemagglutinin; QIV-SD, standard-dose quadrivalent influenza vaccine; TIV, trivalent influenza vaccine; μ g, microgram.

* Vaccination status is determined by information provided by the parent / guardian.

† Dosage selection will be based on the ESDR of the prior Stages. The highest dosage with an acceptable safety review from prior Stages will determine the dose evaluated in Stage 4.

Figure 3.1: Study design flow chart for subjects 6 months to < 5 years of age

[figure not shown]

Figure 3.2: Study design flow chart for subjects 5 to 8 years of age

[figure not shown]
[figure not shown]

Figure 3.3: Study design flow chart for subjects 9 to 17 years of age

3.2 Study Plan

The study plan is summarized in the Table of Study Procedures ([Table 3.2](#), [Table 3.3](#), and [Table 3.4](#)).

Vaccination

All eligible subjects will be randomized to receive 1 or 2 doses of either QIV-HD, Fluarix® Quadrivalent (unadjuvanted QIV-SD), or FLUAD Pediatric® (adjuvanted TIV). The dosage of QIV-HD that is administered will depend on both the age of the subject and the stage at which he / she is enrolled.

- Subjects 9 to 17 years of age will receive 1 dose of the QIV-HD or the comparator vaccine on D0.
- Previously influenza vaccinated subjects 6 months to 8 years of age will receive 1 dose of the QIV-HD or the comparator vaccine on D0.
- Previously influenza unvaccinated subjects 6 months to 8 years of age will receive 2 doses of the QIV-HD or the comparator vaccine. Each dose will be administered 28 days apart (at D0 and D28).

Of note, the highest dosage with an acceptable safety review in prior stages will determine the dose evaluated in Stage 4.

An unblinded administrator at each site will administer the vaccine.

Blood Sampling

Subjects will provide 2 or 3 blood samples, regardless of the stage of enrollment:

- Subjects 9 to 17 years of age will provide a pre-vaccination (baseline) blood sample at V01 (D0) and a post-vaccination blood sample at V03 (D28 [+7 days]) for HAI and SN testing.
Note: Subjects 9 to 17 years of age are scheduled for 2 site visits. However, the second visit is designated as V03 to be consistent with the visits nomenclature of the 6 months to 8 years age groups.
- Previously influenza vaccinated subjects 6 months to 8 years of age will provide a pre-vaccination (baseline) blood sample at V01 (D0) and a post-vaccination blood sample at V03 (D28 [+7 days]) for HAI and SN testing.
- Previously influenza unvaccinated subjects 6 months to 8 years of age will provide a pre-vaccination (baseline) blood sample at V01 (D0) and a post-vaccination blood sample at V03 (D28 [+7 days]) and V05 (28 days after V03 [+7 days]) for HAI and SN testing.

Note: The blood sample will be taken prior to vaccination during any visit when a subject receives a vaccination.

Collection of Safety Data

All subjects will be observed for 30 minutes after vaccination, and any unsolicited systemic adverse events (AEs) occurring during that time will be recorded as immediate unsolicited systemic AEs in the case report book (CRB).

Solicited reactions will be collected up to 7 days after each vaccination, and unsolicited AEs will be collected up to D28 (V03) for subjects receiving 1 dose and up to D56 (V05) for subjects receiving 2 doses. SAEs and AESIs will be collected throughout the study (D0 through approximately 6 months after the last vaccination). It is to be noted that AESIs will be captured as SAEs. These include new onset of Guillain-Barré syndrome (GBS), encephalitis / myelitis (including transverse myelitis), Bell's palsy, convulsions, optic neuritis, and brachial neuritis.

Subjects / parents / guardians will be asked to notify the site immediately about any potential SAEs (including AESIs) at any time during the study.

The study staff will contact subjects 9 to 17 years of age or the subjects' parents / guardians by phone at D8 (+2 days) post-vaccination to identify whether the subject experienced any SAEs not yet reported and will remind the subjects / subjects' parents / guardians to bring the completed diary card with them to V03 (D28 [+7 days]). The study staff will review the D0 to V03 safety data with subjects at V03.

Subjects 6 months to 8 years of age will return to the site at D8 (+2 days) after each vaccination. Staff will review the recorded solicited reactions and unsolicited AEs, and determine whether the subject experienced any SAEs and AESIs not yet reported. Staff will review the safety data with subjects / subjects' parents / guardians at each visit. Staff will also remind the subjects / subjects' parents / guardians to bring the completed diary card with them to the subsequent visit.

The interactive response technology (IRT) system will be used to randomly assign subjects to a study product and to assign subject numbers in each of the groups.

Electronic data capture (EDC) will be used for the collection of data.

Review of safety data

The study will be divided into 4 stages as described in [Section 3.1](#). An ESDR will be conducted for subjects 6 months to 8 years of age. The ESDR will occur following the collection of the safety data at V02 (approximately 8 days post-vaccination) of Stages 1, 2, and 3 by the Safety Management Team (SMT). Enrollment of subjects in the next stage will be initiated if the safety review results are satisfactory. The details of the safety reviews are described in Section 5.1.6 of the protocol.

Table 3.2: Table of Study Procedures 1 (subjects 9 to 17 years of age)

Phase II Study, 2 Visits, 2 Telephone Calls, 1 Vaccination, 2 Blood Samples, approximately 180 Days' Duration per Subject

Visit/Contact	V01	Telephone Call	V03 (Second Visit)*	Telephone Call
Study timelines (days)	D0	D8	D28	180 days after V01
Time windows (days)		+2	+7	+14
Informed consent form / assent form signed and dated	X			
Inclusion / exclusion criteria	X			
Collection of demographic data	X			
Urine pregnancy test (if applicable)†	X			
History of seasonal influenza vaccination	X			
Medical history	X			
Collection of reportable concomitant medications		D0-D28		
Physical examination‡	X			
Randomization / allocation of subject number and unique dose number§	X			
Blood sampling (BL), 5 mL	BL0001**		BL0002	
Vaccination	X			
Immediate surveillance (30 min)	X			
DC provided††	DC1			
DC reviewed and collected			DC1	
Reporting of solicited injection site and systemic reactions		D0-D7		
Collection of unsolicited adverse events		D0-D28		
MA provided††			X	
Study active phase termination record			X	
Follow-up telephone call		X§		X***
Reporting of SAEs (including AESIs)†††	To be reported at any time during the study			

Abbreviations: AESI, adverse event of special interest; BL, blood sampling; D, day; DC, diary card; MA, memory aid; SAE, serious adverse event; V, visit.

* Visit 2 is designated as Visit 3 to be consistent with the visits nomenclature of the 6 months to 8 years age groups.

† For females of childbearing potential. The urine pregnancy test must be performed before vaccination. The pregnancy test must be negative for enrollment.

‡ Targeted physical examination based on medical history will be performed at V01. Targeted physical examination may also be performed at the second visit (designated as V03), if necessary.

§ Before blood sampling and vaccine injection.

** Collection of the blood sample before vaccination.

†† Subjects / parents / guardians will use the diary card to record information about solicited reactions, unsolicited AEs, SAEs, and AESIs from D0 to D7 after vaccination and will continue to record information about unsolicited AEs, SAEs, and AESIs from D8 to the second visit (designated as V03).

†† Subjects / parents / guardians will use this MA to collect information on SAEs and AESIs from V03 (D28 [+7 days]) to the end of the 6- month safety follow-up period.

§§ During this telephone call, staff will record relevant information concerning the subject's health status , will find out whether the subject experienced any SAEs and AESIs not yet reported, and will remind the subjects to bring the completed diary card to the second visit (designated as V03).

*** During this telephone call, staff will review the MA to identify the occurrence of any SAEs and AESIs that have not yet been reported.

††† AESIs will be captured as SAEs. These include new onset of Guillain-Barré syndrome, encephalitis / myelitis (including transverse myelitis), Bell's palsy, convulsions, optic neuritis, and brachial neuritis.

Table 3.3: Table of Study Procedures 2 (previously influenza vaccinated subjects 6 months to 8 years of age)

Phase II Study, 3 Visits, 1 Telephone Call, 1 Vaccination, 2 Blood Samples, approximately 180 Days' Duration per Subject

Visit/Contact	V01	V02	V03	Telephone Call
Study timelines (days)	D0	D8	D28	180 days after V01
Time windows (days)		+2	+7	+14
Informed consent form / assent form (if applicable*) signed and dated	X			
Inclusion / exclusion criteria	X			
Collection of demographic data	X			
History of seasonal influenza vaccination	X			
Medical history	X			
Collection of reportable concomitant medications	D0-D28			
Physical examination†	X			
Randomization / allocation of subject number and unique dose number‡	X			
Blood sampling (BL), 5 mL	BL0001§		BL0002	
Vaccination	X			
Immediate surveillance (30 min)	X			
DC provided**	DC1			
DC reviewed and recorded††		DC1		
DC collected			DC1	
Reporting of solicited injection site and systemic reactions	D0-D7			
Collection of unsolicited adverse events	D0-D28			
MA provided‡‡			X	
Study active phase termination record			X	
Safety follow-up phone call based on MA information§§				X
Reporting of SAEs (including AESIs)***	To be reported at any time during the study			

Abbreviations: AESI, adverse event of special interest; BL, blood sampling; D, day; DC, diary card; MA, memory aid; SAE, serious adverse event; V, visit.

* For children 7 to 8 years of age.

† Targeted physical examination based on medical history will be performed at V01. Targeted physical examination may also be performed at V03, if necessary.

‡ Before blood sampling and vaccine injection.

§ Collection of the blood sample before vaccination.

** Subjects / parents / guardians will use the diary card to record information about solicited reactions, unsolicited AEs, SAEs, and AESIs from D0 to D7 after vaccination and will continue to record information about unsolicited AEs, SAEs, and AESIs from D8 to V03.

†† During V02, staff will review and record D0 to D7 data in the CRB, will find out whether the subject experienced any SAEs and AESIs not yet reported, and will remind the subjects to bring the completed diary card to V03.

‡‡ Subjects / parents / guardians will use this MA to collect information on SAEs and AESIs from V03 to the end of the 6- month safety follow-up period.

§§ During this phone call, staff will review the MA to identify the occurrence of any SAEs and AESIs that have not yet been reported.

*** AESIs will be captured as SAEs. These include new onset of Guillain-Barré syndrome, encephalitis / myelitis (including transverse myelitis), Bell's palsy, convulsions, optic neuritis, and brachial neuritis.

Table 3.4: Table of Study Procedures 3 (previously influenza unvaccinated subjects 6 months to 8 years of age)

Phase II Study, 5 Visits, 1 Telephone Call, 2 Vaccinations, 3 Blood Samples, approximately 208 Days' Duration per Subject

Visit/Contact	V01	V02	V03	V04	V05	Telephone Call
Study timelines (days)	D0	D8	D28	8 days after V03	28 days after V03	180 days after V03
Time windows (days)		+2	+7	+2	+7	+14
Informed consent form signed and dated	X					
Inclusion / exclusion criteria	X					
Collection of demographic data	X					
History of seasonal influenza vaccination	X					
Medical history	X					
Collection of reportable concomitant medications				D0-D56		
Physical examination*	X		X			
Randomization / allocation of subject number and unique dose number†	X					
Allocation of unique dose number			X			
Temporary and definitive contraindications			X			
Blood sampling (BL), 5 mL	BL0001 ‡		BL0002‡		BL0003	
Vaccination	X		X			
Immediate surveillance (30 min)	X		X			
DC provided§	DC1		DC2			
DC reviewed and recorded**		DC1		DC2		
DC collected			DC1		DC2	
Recording of solicited injection site and systemic reactions		D0-D7		D28-D35		
Collection of unsolicited adverse events			D0-D28		D28-D56	
MA provided††					X	
Study active phase termination record					X	
Safety follow-up phone call based on MA information‡‡						X

Reporting of serious adverse events (SAEs) (including AESIs)§§	To be reported at any time during the study
--	---

Abbreviations: AESI, adverse event of special interest; BL, blood sampling; D, day; DC, diary card; SAE, serious adverse event; V, visit.

* Targeted physical examination based on medical history will be performed at V01. Targeted physical examination may also be performed at V03 or V05, if necessary.

† Before blood sampling and vaccine injection

‡ Collection of the blood sample before vaccination.

§ Subjects / parents / guardians will use the diary cards to record information about solicited reactions, unsolicited AEs, SAEs, and AESIs after each vaccination (from D0 to D7 and from D28 to D35) and will continue to record information about unsolicited AEs, SAEs, and AESIs from D8 to V03 and D36 to V05.

** During V02 and V04, staff will review and record D0 to D7 and D28 to D35 data in the CRB, will find out whether the subject experienced any SAEs and AESIs not yet reported, and will remind the subjects to bring the completed diary card to their next scheduled visit.

†† Subjects / parents / guardians will use this MA to collect information on SAEs and AESIs from V05 to the end of the 6- month safety follow-up period.

‡‡ During this phone call, staff will review the MA to identify the occurrence of any SAEs and AESIs that have not yet been reported.

§§ AESIs will be captured as SAEs. These include new onset of Guillain-Barré syndrome, encephalitis / myelitis (including transverse myelitis), Bell's palsy, convulsions, optic neuritis, and brachial neuritis.

4 Endpoints and Assessment Methods

4.1 Safety

See Section 9.1 of the protocol.

4.2 Immunogenicity

See Section 9.2 of the protocol.

4.3 Efficacy

No clinical efficacy data will be obtained in the study.

4.4 Derived Endpoints: Calculation Methods

4.4.1 Safety

4.4.1.1 Solicited Reactions

4.4.1.1.1 Daily Intensity

All daily records for solicited reactions will be derived into daily intensity according to the following classification: None, Grade 1, Grade 2, Grade 3, or Missing.

For measurable injection site reactions (Erythema/Swelling/Induration/Bruising):

- For subjects 6 months to 11 years of age

Grade 1: > 0 to < 25 mm

Grade 2: ≥ 25 to < 50 mm

Grade 3: ≥ 50 mm

- For subjects 12 to 17 years of age

Grade 1: ≥ 25 to ≤ 50 mm

Grade 2: ≥ 51 to ≤ 100 mm

Grade 3: > 100 mm

For measurable systemic reactions (Fever):

- For subjects 6 months to < 36 months of age

Grade 1: $\geq 38.0^{\circ}\text{C}$ to $\leq 38.5^{\circ}\text{C}$, or $\geq 100.4^{\circ}\text{F}$ to $\leq 101.3^{\circ}\text{F}$

Grade 2: $> 38.5^{\circ}\text{C}$ to $\leq 39.5^{\circ}\text{C}$, or $> 101.3^{\circ}\text{F}$ to $\leq 103.1^{\circ}\text{F}$

Grade 3: $> 39.5^{\circ}\text{C}$, or $> 103.1^{\circ}\text{F}$

- For subjects 3 to 17 years of age

Grade 1: $\geq 38.0^{\circ}\text{C}$ to $\leq 38.4^{\circ}\text{C}$, or $\geq 100.4^{\circ}\text{F}$ to $\leq 101.1^{\circ}\text{F}$

Grade 2: $\geq 38.5^{\circ}\text{C}$ to $\leq 38.9^{\circ}\text{C}$, or $\geq 101.2^{\circ}\text{F}$ to $\leq 102.0^{\circ}\text{F}$

Grade 3: $\geq 39.0^{\circ}\text{C}$, or $\geq 102.1^{\circ}\text{F}$

For the derivation of daily intensities the following sequential steps will be applied:

Solicited reactions (except Fever/Pyrexia) with an investigator occurrence recorded as “No” and with all daily records missing then all daily intensities will be derived as “None”.

For non-measurable solicited reactions, daily intensities will correspond to daily records reported in the clinical database. For measurable solicited reactions the daily measurements reported in the clinical database will be converted based upon the intensity scales defined in the protocol; this assumes a reaction that is too large to measure (non-measurable, “NM”) is Grade 3. Note the intensity could be considered “None” (not a reaction) in the analysis despite being considered a reaction by the investigator (eg, swelling measurement > 0 mm but < 25 mm in 12 to 17 years of age).

Note: The maximum intensity on the ongoing period is derived from the record of the maximum intensity/measurement after the end of the solicited period following the rule described above.

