4.4.1.1.3 Occurrence

Occurrence is derived from the maximum intensity on the period considered:

- None: No occurrence
- Grade 1, Grade 2, or Grade 3: Occurrence
- Missing: Missing occurrence

Subjects with at least one non-missing occurrence for a specific endpoint will be included in the analysis. Conversely, those without a non-missing occurrence will not be included in the analysis of the endpoint.

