5.3 Handling of Missing Data and Outliers

5.3.1 Safety

No replacement will be done. Nevertheless, missing relationship will be considered as related at the time of the statistical analysis. No search for outliers will be performed. In all subject listings, partial and missing data will be clearly indicated as missing.

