5.3.1.4 Intensity

For solicited reactions, missing intensities will be handled as described in [Section 4.4.1.1.1](#). For unsolicited non-serious AEs, missing intensities will remain missing and will not be imputed.

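### For most non-fever solicited reactions, a 'No' without daily records is kept as a non-reactor but a 'Yes' without daily records is dropped, so the any-grade rate is biased downward when this occurs

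*SAP*

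**What the plan says.** SAP 4.4.1.1.1 derives daily intensities in sequential steps.

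- The first step opens with "Solicited reactions (except Fever/Pyrexia) with an investigator occurrence recorded as" a negative answer. In that case the rule is that "with all daily records missing then all daily intensities will be derived as" the class None.
- The next step covers everything else. Reactions without a size, such as malaise, have this rule: "For non-measurable solicited reactions, daily intensities will correspond to daily records reported in the clinical database". The sized injection site reactions and temperature have a parallel one: "For measurable solicited reactions the daily measurements reported in the clinical database will be converted based upon the intensity scales defined in the protocol", with a reaction too large to measure taken as Grade 3.

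No step mentions an investigator answer of 'Yes'.

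SAP 4.4.1.1.2 takes maximum intensity from the daily intensities. SAP 4.4.1.1.3 continues: "Occurrence is derived from the maximum intensity on the period considered". A missing maximum gives a missing occurrence, and "those without a non-missing occurrence will not be included in the analysis of the endpoint".

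The missing-data section adds no rule. SAP 5.3.1.4 refers back: "For solicited reactions, missing intensities will be handled as described in" 4.4.1.1.1. SAP 5.3.1 states: "No replacement will be done. Nevertheless, missing relationship will be considered as related at the time of the statistical analysis".

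**The concern.** The SAP accepts the investigator's answer in place of daily records when the answer is 'No' but makes no use of it when the answer is 'Yes'. Take two children with no daily records. One parent tells the site there was no malaise, and the child counts as 0 of 1. The other reports malaise but cannot give daily grades, and the child is not counted. Whether a child enters the analysis then depends on the outcome being measured.

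The SAP treats comparable safety gaps differently. Under 4.4.1.2.1 an unsolicited event counts once it has a verbatim term and is not Grade 0, and under 5.3.1.4 its missing intensity simply stays missing. A missing relationship is taken as related, which is the cautious direction. Dropping a reported solicited reaction goes the other way.

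Describing the safety of each dosage is the trial's safety objective, and the study is meant to select the dosage for Phase III. Solicited reactions are a main part of that description, and many arms have only 30 or 10 children.

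**Working it through.** The plan states no expected reaction rate and no missing-diary rate, so there is no figure to reproduce. The check traces the rules and then computes the effect.

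**Trace for a non-fever reaction with no daily records**

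| Step | Answer 'No' | Answer 'Yes' |
|---|---|---|
| Daily intensity (4.4.1.1.1) | None on all days | Missing on all days |
| Maximum intensity (4.4.1.1.2) | None | Missing |
| Occurrence (4.4.1.1.3) | No occurrence | Missing |
| Any-grade rate | In denominator, not in numerator | In neither |

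**Inputs.** Arm sizes of 30 QIV-HD and 10 QIV-SD come from the 3:1 groups (SAP Table 3.1 and 5.5). The number of reactors x, and the number k of them with 'Yes' and no daily records, are assumptions.

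**Formula.** The SAP rule gives (x-k)/(n-k). The shortfall against x/n is

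x/n - (x-k)/(n-k) = k(n-x) / [n(n-k)],

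which is positive whenever k > 0 and x < n. For x = 3, n = 30, k = 1 it is 27/(30 × 29) = 3.1 points. For x = 3, n = 10, k = 1 it is 7/(10 × 9) = 7.8 points.

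| All counted, x/n | k = 1 | k = 2 | k = 3 |
|---|---|---|---|
| 3/30 = 10.0% | 2/29 = 6.9% | 1/28 = 3.6% | 0/27 = 0.0% |
| 9/30 = 30.0% | 8/29 = 27.6% | 7/28 = 25.0% | 6/27 = 22.2% |
| 15/30 = 50.0% | 14/29 = 48.3% | 13/28 = 46.4% | 12/27 = 44.4% |
| 3/10 = 30.0% | 2/9 = 22.2% | 1/8 = 12.5% | 0/7 = 0.0% |

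The Clopper-Pearson 95% intervals are 2.1 to 26.5% for 3/30, 0.8 to 22.8% for 2/29, 6.7 to 65.2% for 3/10 and 2.8 to 60.0% for 2/9.

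**As a share.** If a share a of true reactors is affected, a true rate p is reported as p(1-a)/(1-pa). For assumed a of 5%, 10% and 20%, a true 10% is reported as 9.5%, 9.1% and 8.2%, and a true 30% as 28.9%, 27.8% and 25.5%.

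**Dropping both answers instead.** With x = 15 and n = 30, dropping one 'Yes' and one 'No' gives 14/28 = 50.0%, which is unbiased. Dropping one 'Yes' and three 'No' gives 14/26 = 53.8%. Excluding both answers is therefore unbiased only if records are missing in equal proportion among reactors and non-reactors. Using both answers gives 15/30 in either case.

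**The case against.** **The answers are not mirror images.** 'No' fixes every daily intensity, whereas 'Yes' fixes neither grade, onset nor number of days, so leaving those missing agrees with the no-replacement rule. This is right for grade and timing. It does not hold for any-grade occurrence, which 'Yes' does settle.

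**The case should be rare.** On a natural reading of the maximum, one graded day is enough to keep the child. Staff review diaries at V02 and V04 in children up to 8 years (protocol 5.1.4), interview families about incomplete entries and must explain missing data (11.1), run consistency checks (11.2), obtain verbal clarification (13.2) and close queries before lock (13.4.1). SAP 5.6 adds a blind review with a statistical component. This stands and limits the size. At 9 to 17 years the first diary review is at V03, nominally 21 days after the solicited window closes. With k = 0 there is no bias, and in the examples with k = 1 the intervals overlap widely.

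**The rule is inferred from silence.** The SAP never says that 'Yes' with no records is excluded. That is so, but its steps allow no other result.

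A reader might also infer more than the documents support:

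- *That all solicited reactions are biased downward.* Fever is excepted from the 'No' rule, so both answers without temperatures are missing and this asymmetry does not arise. The early safety data review's Grade 3 fever criterion is untouched. For erythema, swelling, induration and bruising at 12 to 17 years, a reaction under 25 mm is scored None. A dropped 'Yes' may then be a non-event, and the rate rises: 3/30 = 10.0% becomes 3/29 = 10.3%. The direction is not fixed for these four.
- *That differences from QIV-SD shrink.* With the same a in both arms the reported odds are p(1-a)/(1-p), so the odds ratio is unchanged. For 30% against 10% at a = 10%, the risk ratio moves from 3.00 to 3.06, away from 1, while the risk difference falls from 20.0 to 27.8 - 9.1 = 18.7 points. For 70% against 60% the risk difference widens from 10.0 to 10.3 points. SAP 5.1.1.2.1 plans single proportions only for safety, with no between-arm estimate.

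**Conclusion.** The point holds for solicited reactions other than fever and other than the four measured injection site reactions at 12 to 17 years. Followed as written, the SAP drops known reactors and keeps matching non-reactors. The any-grade rate in an arm is then too low whenever a 'Yes' with no daily records occurs and not every child in the arm reacted. One such child costs 3.1 points at 3/30 and 7.8 points at 3/10.

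This rests on three assumptions: that the database can hold 'Yes' with blank days, as the SAP already foresees for 'No'; that the investigator's answer is correct; and that the SAP's silence is read through its own steps. The number of cases is unknown and probably small. No conclusion is drawn about between-arm differences or the fever criterion. The gap is still worth closing, because the direction is known and the correction is cheap.

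**What to change.** Add to SAP 4.4.1.1.1 and 4.4.1.1.3:

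*A solicited reaction other than fever with investigator occurrence Yes and all daily records missing is counted as an occurrence with missing intensity, in the numerator and denominator of the any-grade rate. Exception: for erythema, swelling, induration and bruising at 12 to 17 years, where under 25 mm is not a reaction, occurrence stays missing, the subject is outside the denominator, and the number of such subjects is reported.*

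Add a Missing category to the intensity tables and to the time-of-onset and days-of-occurrence tables (SAP Tables 4.1 and 4.2 have none; Table 4.3 already does). Report the number of affected subjects per arm, so that readers can see whether the rule mattered.

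The cost is a short SAP addition and a few table rows, with no new data collection. The downside is slightly higher reported rates and a few occurrences without grade, onset or duration. If the count is zero, no result changes.
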